100 sub-acute patients (including inpatients and outpatients) will be recruited from the National Taiwan University Hospital. The patients will meet the criteria (both inclusion and exclusion criteria) mentioned in the phase 4 study. Their caregivers will also be invited to participate.

Power analysis

A difference of 2 points (about 10%) on the Barthel index in favor of the experimental group will be regarded as clinically relevant.⁵⁷ In addition, we expect that about 70% of the participants will complete all assessments. Therefore, about 50 patients will be required for each arm of the trial to achieve a sufficient statistical power of 80%.

Procedure:

The patients will be randomly assigned into an experimental group (receiving the patient-centered program) or a control group (receiving additional rehabilitation). Allocation concealment will be applied. All participants will be assessed by trained raters at the beginning of the study, 4 weeks after inception of the study, 3 months after inception of the study, and 1 year after inception of the study. The raters will be unaware of study-group assignment. The cost of each group will be recorded.

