We will determine cost-effectiveness by relating the costs to the effects of the program. The effects will be expressed as quality-adjusted life years (QALYs), which are measured by the EQ-5D. The costs include the costs related to resource use of primary care clinicians, secondary care appointments, admissions to health care facilities, community-based support, and individual out-of-pocket expenditure (direct costs). The direct cost estimates will be based on the costs of hospital stay and follow-up rehabilitation care. Medication costs and costs related to assistive devices and adaptations in and around the house will also be included. The costs of productivity losses (indirect costs) will not be counted because most stroke patients are retired. The incremental cost-effectiveness ratio will be calculated by dividing the mean difference in costs by the mean difference in effect (as measured by the EQ-5D) between the two groups. Costs will be evaluated by having each patient keep a cost diary for the first 24 weeks after randomization. A research assistant will check the diary every other day to ensure the integrity of recording (including the time spent on each kind of professional care). The hourly costs of specialists (including physicians, physical therapists, occupational therapists, and speech and language therapists) will be calculated using the salary schedules at the National Taiwan University Hospital.

The patient-centered program will last for 6 weeks. We expect that the therapist will spend 2-4 hours on each patient per week. For the control group, we will provide 2-hour OT per week in addition to the original OT. The content of the original and additional OTs will be recorded for both groups.

Neurobehavioral conditions of the patients:

The NIHSS⁵¹ will be used to indicate stroke severity in the study sample. The NIHSS is a well validated and commonly used stroke impairment scale that sums the scores from individual elements of the neurological examination to provide an overall stroke severity score.^{51,58}

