The participants in the control group will not be given the results of testing. However, oral explanations will be given by the research assistant if they have questions about the testing. These participants in the control group will be offered additional rehabilitation programs to serve as placebo. The time of the additional rehabilitation program will be similar to the time that the participants spend taking part in the experimental group, which we expect to be about 2 hours per week for 3 consecutive weeks.

Data analysis:

Baseline characteristics will be reported by descriptive statistics (e.g., mean and SD for continuous variables, or frequency tabulations for categorical variables) for each group. Homogeneity of both groups at the baseline (time 1) will be examined using a Student's t test or Mann-Whitney U test where appropriate. If there are between significant differences between both groups, statistical control (e.g., analysis of covariance, ANCOVA) will be applied for further analysis of effectiveness.

The primary analysis of effectiveness (full-analysis set) will consist of a comparison of the change scores between time 2 to time 1 and time 3 to time 2 in primary and secondary outcome measures. Analysis of variance (ANOVA) will be used to compare the change scores between groups. The analyses will be adjusted using ANCOVA for any significant differences at baseline. Intention-to-treat analysis will be applied. Alpha level will be set at 0.05. The statistical analyses will be done by use of SPSS (version 16.0).

Incremental cost-effectiveness ratios will be calculated as cost per QALY to assess the cost-effectiveness of the different programs.

(F) Anticipated Results

We expect that the patients and caregivers' original knowledge of stroke and OT would be limited or modest. Our adaptive knowledge and education system will efficiently improve their knowledge of stroke and OT. We anticipate that the CATs for stroke and OT knowledge can reach an overall reliability above 0.95 (i.e., excellent reliability) and require less than 10 minutes to administer or test fewer than 20 items to ensure its efficiency.

Furthermore, the patient-centered OT program using the adaptive knowledge and education system will improve ADL independence in stroke patients. The patient-centered OT program will be cost-effective in increasing ADL function and quality-adjusted life years.

Significance:

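### Phase 6 gives two incompatible therapy times, so the stated similarity of time between arms is not secured

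*Protocol*

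**What the plan says.** All references are to the Protocol, Research Design and Methods.

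- **Phase 6, Procedure, allocation.** "The patients will be randomly assigned into an experimental group (receiving the patient-centered program) or a control group (receiving additional rehabilitation"). The experimental condition is therefore the whole programme.
- **Phase 6, Procedure, dose.** "The patient-centered program will last for 6 weeks. We expect that the therapist will spend 2-4 hours on each patient per week". The next sentence reads: "For the control group, we will provide 2-hour OT per week in addition to the original OT". It gives no number of weeks. Then: "The content of the original and additional OTs will be recorded for both groups".
- **Phase 6, Treatment protocols for the experimental and control groups.** This section describes the knowledge test and education cycle, expected to take 2 to 3 weeks. Controls are "offered additional rehabilitation programs to serve as placebo", and the time is to be similar to that spent "taking part in the experimental group, which we expect to be about 2 hours per week for 3 consecutive weeks".
- **Phase 4, Protocols for the experimental and control groups.** The same control paragraph appears almost word for word. There the experimental group receives only the computerised knowledge and education system.
- **Phase 5.** The education system is placed inside one of six components of the patient-centred programme.
- **Phase 6, follow-up and analysis.** After baseline, assessments fall "4 weeks after inception of the study, 3 months after inception of the study, and 1 year after inception of the study". The primary analysis is a "comparison of the change scores between time 2 to time 1 and time 3 to time 2 in primary and secondary outcome measures".

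**The concern.** Two parts of the Phase 6 text give different lengths and total hours for the same experimental arm. The control dose is pegged to that arm's time. The only control duration written anywhere in Phase 6 is the 3 weeks that fitted Phase 4, and it does not fit a 6-week programme. Therapists or study staff working from one section or the other could deliver different amounts of control therapy.

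This matters because the comparator is meant to equalise time. The Background section on the possible effects of stroke/OT education credits OT itself with improving ADL independence, and the Phase 6 primary outcomes are measures of basic and instrumental ADL. If the arms differ in therapy hours, a difference between them cannot be put down to patient-centred content alone. Control therapist hours also enter the cost comparison, since Procedure costs specialists by the hour.

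**Working it through.** **Inputs**

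| Quantity | Value | Source |
|---|---|---|
| Experimental time, first statement | 2–4 therapist h/week, 6 weeks | Phase 6, Procedure |
| Experimental time, second statement | about 2 h/week, 3 weeks | Phase 6, Treatment protocols |
| Control extra OT, rate | 2 h/week | both sections |
| Control extra OT, duration | not stated / 3 weeks | Procedure / Treatment protocols |

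**Step 1. The plan's own figure.** Total hours = hours per week × weeks. Treatment protocols: 2 × 3 = 6 h in the experimental arm and, by matching, about 6 h in control. Taken alone, this section implies a gap of 0.

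**Step 2. The other statement for the same arm.** Procedure: 2 × 6 = 12 h to 4 × 6 = 24 h. The 6 h figure is 6/24 = 25% to 6/12 = 50% of that. The two sections agree on the control rate. They disagree on experimental duration, and agree on the experimental weekly rate only at the bottom of the 2–4 h range.

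**Step 3. Gap between arms (experimental minus control), with the programme as in Procedure.**

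- Control for 6 weeks: 2 × 6 = 12 h. Gap = 12 − 12 = 0 to 24 − 12 = 12 h.
- Control for 3 weeks: 2 × 3 = 6 h. Gap = 12 − 6 = 6 to 24 − 6 = 18 h.

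A zero gap occurs at only one point: programme at 2 h/week and control for 6 weeks.

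**Step 4. Where the gap falls relative to the 4-week assessment**, if the programme starts at study inception. Experimental hours are 4 × 2 = 8 to 4 × 4 = 16 by week 4, and 2 × 2 = 4 to 2 × 4 = 8 in weeks 5–6.

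- Control for 6 weeks (8 h by week 4, 4 h after): gap 0–8 h before and 0–4 h after.
- Control for 3 weeks (6 h by week 3, none after): gap 2–10 h before and 4–8 h after.

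Either change score in the primary analysis can therefore carry a difference in therapy time. Under the 6-week reading that difference can also be zero.

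**The case against.** The strongest reply is that the Treatment protocols section times only the education cycle, which Phase 5 places within one programme component. On that view the 2–3 week cycle and the 6-week programme do not conflict, and the 3-week control schedule was never meant for the whole trial. Procedure also gives the 6 weeks, the experimental hours and the control hours in consecutive sentences, so 6 weeks is the natural control duration. Both sections frame these times as expectations, and detailed procedures were to be developed in Phase 5.

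Much of this stands. The 2–3 week education cycle is not itself an error, and the 3-week control reading is the less likely one. But the time sentence is not limited to education: it refers to the experimental group, which Procedure defines as receiving the full programme. Even with 6 control weeks, the times are equal only at the bottom of the 2–4 h range.

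A second reply also stands in part. Procedure counts hours the therapist gives, Treatment protocols counts time the participant spends, and a research assistant runs the education. The gaps above depend on treating these as comparable.

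Three stronger inferences are tempting and not supported:

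- **Control is short by 6–18 h and the result is biased by that amount.** This takes the less likely reading as fact and equates the two kinds of hours.
- **The programme replaces original OT, so control might receive more therapy.** The protocol does not say outright that the 2–4 h is additional, but the plan to record original and additional OT in both groups points that way, and no amount of original OT is given.
- **Different centres could deliver different doses.** Phase 6 recruits from one hospital, so any variation would be between staff there.

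**Conclusion.** Wrong as written, and worth fixing. Phase 6 states the experimental arm's time as 6 h in one section and 12–24 h in another, and it pegs the control dose to the figure that does not fit the programme. The excess of experimental over control time is 0–12 h if control runs 6 weeks and 6–18 h if it runs 3. Both ranges assume that therapist and participant hours are comparable and that the 2–4 h comes on top of original OT. The inconsistency in the text is certain. The existence and size of any bias are not established. What follows is narrower: the claim of similar time is not secured, so an ADL gain could partly reflect therapy time and should not be credited to patient-centred content alone.

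**What to change.** 1. In Phase 6, Treatment protocols, replace the 3-week sentence: control's extra OT runs the same 6 weeks as the programme at a dose fixed in advance, 2 h/week as in Procedure.
2. Label the 2–3 week text in that section as the education component only.
3. In Procedure, state the number of control weeks and, if intended, that the programme's 2–4 h is additional to original OT.
4. If control stays at 2 h/week while the programme may reach 4 h/week, delete the similar-time claim, report recorded therapy hours by arm, and interpret the result as programme plus any extra therapy time. The individual 2–4 h range can stay, since the programme is tailored.

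Matching control to the average time actually delivered in the experimental arm is not a workable rule: the arms run concurrently and that average is unknown in advance.

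**Cost.** The text changes are free, and Procedure already has time per kind of professional care recorded. With 50 control patients and one-to-one sessions assumed, running control for 6 weeks rather than 3 adds (12 − 6) × 50 = 300 therapist hours if only 3 weeks had been intended, and none if Procedure already meant 6. The remaining cost is a slightly less favourable interpretation under item 4.

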1. To examine the model-data fitting of the items and calibrate the item characteristics with Rasch modeling. The fitted and calibrated items will serve as the item bank of the computerized adaptive testing system for stroke and OT knowledge.
2. To determine the performance (i.e., number of items needed to achieve excellent reliability) of the computerized adaptive testing system via a simulation study.
3. To develop a personal computer version of the computerized adaptive knowledge and education system to be used for the subsequent data collection.

Phase 4 - The third year (2-3; 1 year):

1. To examine the effectiveness of on 50 patients and 50 caregivers.

Phase 5 - The last 3 months of the third year (3; 0.25 year):

1. To develop the treatment protocol of patient-centered, individual tailored OT on the basis of the

computerized adaptive knowledge and education system. We will ensure that the protocols are feasible.

Phase 6 - The fourth year and the fifth year (4-5; 2 years):

1. To examine the effectiveness of the treatment protocol of patient-centered, individual tailored OT on 100 patients. Both short-term and long-term effects will be determined.
2. To determine the cost effectiveness and cost utility of the protocol of patient-centered OT.

(B) Statement of Qualifications for Innovative Research Grant Award

N/A

(C) Background and Significance

The importance of ADL function for stroke patients

Stroke is the leading cause of adult disability.¹ A patient's performance of activities of daily living (ADL) is considered indicative of the level of concomitant disability (or independence), which is often an outcome measure in stroke trials.^{2, 3} ADL dependence (i.e., disability) of a stroke patient often leads to burden and stress on his/her caregiver and dissatisfaction with life.^{4, 5} Thus, the quality of life of both patients and caregivers is highly threatened following a stroke.⁶

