Baseline characteristics will be reported by descriptive statistics (e.g., mean and SD for continuous variables, or frequency tabulations for categorical variables) for each group. Homogeneity of both groups at the baseline (time 1) will be examined using a Student's t test or Mann-Whitney U test where appropriate. If there are between significant differences between both groups, statistical control (e.g., analysis of covariance, ANCOVA) will be applied for further analysis of effectiveness.

The primary analysis of effectiveness (full-analysis set) will consist of a comparison of the change scores between time 2 to time 1 and time 3 to time 2 in stroke and OT knowledge. Analysis of variance (ANOVA) will be used to compare the change scores between groups. The analyses will be adjusted using ANCOVA for any significant differences at baseline. Intention-to-treat analysis will be applied. Alpha level will be set at 0.05. The statistical analyses will be done by use of SPSS (version 16.0).

Phase 5: Developing a patient-centered OT program.

We will develop a patient-centered, individual tailored OT program on the basis of both a theoretical framework and the opinions of clinical experts. We will employ Steward et al.'s model³⁰ to develop the patient-centered OT program. The 6 main components of Steward et al.'s model include: (1) exploring both disease and illness experience, (2) understanding the whole person, (3) finding common ground, (4) incorporating prevention and health promotion, (5) being realistic, and (6) enhancing the patient-clinician relationship.³⁰ We will develop detailed procedures for administering all the components, as an individual and as a whole. The computerized adaptive stroke and OT knowledge and education systems will be included in the component of "exploring both disease and illness experience." We will invite 5 occupational therapists with sufficient clinical experience and 2 psychiatrists to review the procedures of the patient-centered, tailored OT program. Their comments will be used to revise the procedures until agreement has been reached.

After the procedures for the patient-centered OT program are developed, we will test the feasibility of the program. We will make revisions where necessary. The clinical experts will be consulted if necessary.

Phase 6: Examining the effectiveness the patient-centered OT program on 100 patients.

Subjects:

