The EuroQol is a generic measure of quality of life (QoL) and consists of a health status profile in five domains (EQ-5D), including two that are directly related to self-care and mobility.⁷² The EuroQol has been validated for use in stroke patients.⁷³ The advantage of the EuroQol is that it can be transformed into a utility score, allowing cost-utility analysis.^{43, 72}

The Stroke-Specific Quality of Life (SS-QOL)¹ is the first HRQOL measure designed to capture all domains meaningful for stroke patients. The original developers constructed the domains and items of the SS-QOL on the basis of patient interviews. It originally included 49 items from 12 domains. We have reported that construct validity of the 12-domain SS-QOL is well supported for measuring HRQOL in ischemic stroke patients.⁷⁴

Treatment protocols for the experimental and control groups:

The patients assigned to the experimental group will first receive the computerized adaptive knowledge testing system. They will be then given adaptive educational materials provided by the educational system according to their testing results. The participants will be instructed to read or watch the educational materials. A research assistant will help them use the system and offer counseling/explanations for the materials. The patient and caregiver will be given a week to learn these materials. Further counseling/explanations will be given, if necessary. After a week, the research assistant will ask the participants whether they have further questions on the educational materials. The research assistant will answer their remaining questions until the participants are satisfied with the explanations. Then the participants will be asked to take the computerized knowledge testing system again. Further educational materials will be offered, if necessary. The testing and educational procedures will continue until the participants' stroke and OT knowledge has reached a satisfactory level. The research assistant will make sure that the participants understand all the fundamental knowledge of stroke and OT, which will be pre-determined by our experts.

We expect that the whole procedure will take about 2 to 3 weeks (i.e., two to three times of education). The time that the patient/caregiver devotes to learning the related materials will be recorded. We will also document the difficulties/questions raised by the participants. Such information will be useful for further improving the efficiency the system.

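### The Phase 6 primary contrasts omit the 1-year visit and never compare 3 months with baseline, so the stated analysis does not test the long-term aim.

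*Protocol*

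**What the plan says.** Section (A), Specific Aims, says of Phase 6: "Both short-term and long-term effects will be determined". Section (E), Phase 6, Procedure, schedules an assessment at the beginning and then "4 weeks after inception of the study, 3 months after inception of the study, and 1 year after inception of the study".

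The Phase 6 Data analysis paragraph defines only the first time point: "Homogeneity of both groups at the baseline (time 1) will be examined". It then fixes the primary effectiveness analysis as a "comparison of the change scores between time 2 to time 1 and time 3 to time 2 in primary and secondary outcome measures", with the test "Analysis of variance (ANOVA) will be used to compare the change scores between groups".

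The Phase 4 Data analysis paragraph is almost the same: a "comparison of the change scores between time 2 to time 1 and time 3 to time 2 in stroke and OT knowledge". Phase 4 has only three visits: the start, 4 weeks and 3 months.

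On duration, Phase 6, Procedure, says "The patient-centered program will last for 6 weeks". The Phase 6 treatment protocols say of the testing and education cycle "We expect that the whole procedure will take about 2 to 3 weeks", and they expect the control sessions to run for 3 consecutive weeks.

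**The concern.** Four visits are planned, but the primary analysis names three times. In visit order, time 2 is 4 weeks, time 3 is 3 months, and the 1-year visit has no place in any stated effectiveness comparison. The protocol therefore collects the data its long-term aim needs without saying how they will answer that aim.

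The second contrast also starts from week 4 and not from baseline. If it is read as an effectiveness result, as the paragraph invites, a benefit that persists in full appears as no difference. A benefit that is smaller at 3 months but still present appears as a disadvantage. At stake are how the trial's main result is interpreted and whether one of its stated aims is tested at all.

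**Working it through.** **What the contrasts estimate.** Let D2, D3 and D12 be the between-arm differences in mean change from baseline at 4 weeks, 3 months and 1 year.

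- Time 2 minus time 1 estimates D2.
- Time 3 minus time 2 estimates D3 − D2.
- Their sum is D3, so the 3-month effect can be derived, but neither contrast tests it.
- D12 cannot be obtained from times 1 to 3.

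If a benefit is kept in full, D3 = D2 and the second contrast is 0. If an assumed 2-point benefit at week 4 falls to 1 point at 3 months, the second contrast is 1 − 2 = −1, although the experimental arm is still 1 point ahead. This part needs no assumption about variance.

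**Inputs for an illustration of size.** Phase 6, Power analysis, gives 50 patients per arm, about 70% completing all assessments, a 2-point Barthel difference and 80% power. Data analysis gives alpha 0.05; I assume it is two-sided. Completers per arm: 50 × 0.70 = 35.

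**The plan's own figure.** The 50 per arm cannot be reproduced because no SD is stated. Solving for the SD that gives 80% power:

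- Normal approximation: SD = 2 / [(1.960 + 0.842) × √(2/35)] = 2 / (2.802 × 0.239) ≈ 2.99.
- Two-sample t-test: SD ≈ 2.94.

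**Power of the contrasts.** Assume a true 2-point effect at 3 months and the same SD for every contrast. The standardised effect is δ / (SD × √(2/35)). Either SD gives essentially the same powers.

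| Assumed build-up | Time 2 − time 1 | Time 3 − time 2 | Time 3 − time 1 (not planned) |
|---|---|---|---|
| Linear over 6 weeks, then stable | 2 × 4/6 = 1.33 points: 46% | 2 − 1.33 = 0.67 points: about 15% | 2 points: 80% |
| Half by week 4 | 1 point: 29% | 1 point: 29% | 2 points: 80% |
| Complete by week 4, then kept | 2 points: 80% | 0 points: 5% (false-positive rate) | 2 points: 80% |

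In the linear case, the chance that at least one planned contrast is significant is about 55% to 59%. That range takes the correlation between the two changes as 0 or −0.5 and makes no multiplicity correction. No power can be given for 1 year, because no test is stated for it.

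**Sensitivity.** If change over the first 4 weeks varied less, the 1.33-point contrast would have about 59% power at SD 2.5 and about 78% at SD 2.0.

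**Timing of week 4.** Against the 6-week programme, week 4 is 2 weeks before the end. Against the 2 to 3 weeks of education and 3 weeks of control sessions, it comes after them.

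**The case against.** The strongest reply has five parts.

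- **The 1-year data may still be analysed.** The paragraph fixes the primary analysis and does not exclude others. A statistical analysis plan not at hand may add one, and the EQ-5D feeds a cost-per-QALY analysis with no stated horizon. So a reader who infers that the 1-year visit will never be analysed goes further than the text. What stands is that the protocol names its effectiveness contrasts and the visit its long-term aim needs is not among them. The cost diary covers only 24 weeks, so the economic analysis does not clearly fill the gap.
- **A lasting benefit need not be missed.** If the effect is complete by week 4, time 2 minus time 1 detects it with 80% power in the illustration. The inference that a real benefit would generally fail both contrasts is not supported; the loss depends on gradual build-up.
- **Week 4 may not be mid-treatment.** It is tempting to call time 2 an on-treatment reading. That holds on the 6-week figure but not on the shorter figures in the treatment protocols, so the documents do not settle it.
- **Phase 4 is a different case.** There the education is expected to take 2 to 3 weeks and time 2 is week 4, so time 2 minus time 1 is sound and time 3 minus time 2 is a legitimate maintenance question. It does not misstate retention. The weakness is that it is presented as effectiveness, with no 3-month change from baseline beside it.
- **The power figures are soft.** The SD is back-solved and applied equally to every interval. The Barthel Index is not itself listed as a primary outcome; the Frenchay index, the combined ADL score (which includes the Barthel items) and the adaptive ADL test are. This is correct, and the figures are offered only as illustrations.

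The close match with the Phase 4 wording suggests that the paragraph was reused without the fourth visit. The protocol does not say so, and the point does not need it.

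**Conclusion.** The point holds as an inconsistency between the Phase 6 aim, its visit schedule and its stated primary analysis. It should be corrected before the analysis is fixed. Two parts rest on the text and simple algebra alone: no stated effectiveness contrast uses 1 year or sets 3 months against baseline, and time 3 minus time 2 measures change in the effect, not the effect. The only inference is that times 2 and 3 follow visit order, since only time 1 is defined. Three contiguous or other labels would still leave one of the four visits out.

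The size of any power loss is conditional on the assumed SD and course of effect: substantial if the effect builds gradually, none for time 2 minus time 1 if it is complete by week 4.

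**What to change.** In Phase 6, Data analysis:

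- Replace the two contrasts with between-arm differences in change from baseline at 4 weeks, 3 months and 1 year.
- Name one of these in advance as primary, and tie the 2-point power calculation to it with a stated SD.
- Name 1 year versus baseline as the long-term contrast.
- Keep time 3 minus time 2, if wanted, only as a labelled maintenance contrast.
- Define every time label by its visit.

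In Phase 4, Data analysis, keep time 2 minus time 1, add time 3 minus time 1, and label time 3 minus time 2 as maintenance.

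Separately, reconcile the 6-week programme in Phase 6, Procedure, with the 2 to 3 weeks of education and 3 weeks of control sessions in the treatment protocols, so that it is clear what the week-4 reading represents.

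The cost of the contrast changes is analysis wording in two paragraphs. Every visit is already scheduled, so no patients or assessments are added.
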